### **13.2 Risks associated with use of the Aptar CPS device**

The Aptar CPS device has been extensively characterized and found to be safe for use. Participants could experience some discomfort to their eyes or face if they do not hold the device to their nose as directed; however, again, the study nurse will carefully instruct the participant regarding device use so that any errors can be immediately corrected.

### **13.3 Risks associate with use of the Empatica E4 actigraphy device**

Rarely, skin irritation may occur in reaction to the wristband or sensors.

### **13.4 Risks associated with use of the Libre Freestyle Pro Glucose Monitoring System**

The CGM is FDA-approved and widely used for assessing glucose levels in diabetes. The following are possible adverse effects of inserting a sensor and wearing the adhesive patch: local erythema (redness), local infection, inflammation, pain or discomfort, bleeding at the glucose sensor insertion site, bruising, itching, scarring or skin discoloration, hematoma, and adhesive irritation. There is a remote risk of sensor or needle fracture during insertion, wear or removal, with fragments retained under the skin.

### **13.5 Lumbar Puncture**

Lumbar puncture may be associated with pain during the performance of the procedure. This is usually temporary and confined to the lower back. Headache may occur in about 5% of elderly people who undergo lumbar puncture. Less commonly, in about 1-4% of participants, a persistent low-pressure headache may develop, probably due to leakage of CSF. Lower rates of post-LP headache have been noted in elderly patients, and when atraumatic (Sprotte) needles are used. If a post-LP headache persists it may need additional treatment, e.g. with fluids and analgesics. Uncommonly a blood patch (injection of some of the participant's blood to patch the CSF leak) may be needed. Potential but rare risks of lumbar puncture include infection, damage to nerves in the back, and bleeding into the CSF space. The risk of these is much less than 1%.

### **13.6 Blood Draw**

The risks of blood draw include pain from the needle, bruising or infection at the site of venipuncture, or fainting as a response to blood draw. Approximately 100 mLs of blood will be drawn for routine and biomarker laboratory assessments over the course of this study.

## 15.0 STUDY DRUGS

Participants will take empa or placebo 30 minutes before breakfast daily. Participants will also take four doses of INI (40 International Units per dose) or placebo 30 minutes before each meal and 30 minutes before bedtime.

### 15.1 Humulin® R U-100 Insulin

Humulin® R U-100 (NDC: 0002-8215, Eli Lilly & Company) is a polypeptide hormone structurally identical to human insulin synthesized through rDNA technology in a special non-disease-producing laboratory strain of *Escherichia coli* bacteria. Humulin R U-100 has the empirical formula  $C_{257}H_{383}N_{65}O_{77}S_6$  and a molecular weight of 5808 Da. Humulin R U-100 is a sterile, clear, aqueous, and colorless solution that contains human insulin (rDNA origin) 100 units/mL, glycerin 16 mg/mL and metacresol 2.5 mg/mL, endogenous zinc (approximately 0.015 mg/100 units) and water for injection. The pH is 7.0 to 7.8. Sodium hydroxide and/or hydrochloric acid may be added during manufacture to adjust the pH.

More information about the Humulin® R U-100 insulin, including risks, contraindication and adverse reactions can be found in the the US package insert (USPI).

### 15.2 Empagliflozin

Empagliflozin (Jardiance, Boehringer-Ingelheim) is a sodium glucose co-transporter2 inhibitor. The chemical name of empagliflozin is D-Glucitol,1,5-anhydro-1-C-[4-chloro-3-[[4-[[3S)-tetrahydro-3-furanyloxy]phenyl]methyl]phenyl]-, (1S). Its molecular formula is  $C_{23}H_{27}ClO_7$  and the molecular weight is 450.91. Empagliflozin is a white to yellowish, non-hygroscopic powder. It is very slightly soluble in water, sparingly soluble in methanol, slightly soluble in ethanol and acetonitrile; soluble in 50% acetonitrile/water; and practically insoluble in toluene. Each film-coated tablet of JARDIANCE

contains 10 mg empagliflozin (free base) and the following inactive ingredients: lactose monohydrate, microcrystalline cellulose, hydroxypropyl cellulose, croscarmellose sodium, colloidal silicon dioxide and magnesium stearate. In addition, the film coating contains the following inactive ingredients: hypromellose, titanium dioxide, talc, polyethylene glycol, and yellow ferric oxide.

More information about empagliflozin can be found the prescribing information included on the Jardiance/Boehringer-Ingelheim website:

<https://docs.boehringer-ingelheim.com/Prescribing%20Information/PIs/Jardiance/jardiance.pdf>

## **15.2 Randomization**

Eligible participants will be randomized on a 1:1 schedule to placebo (insulin diluent; placebo capsule), INI, empa, or INI+empa. Randomization will be stratified by diagnosis (normal, MCI or AD)

## **15.3 Blinding**

Neither participants nor site personnel involved in assessing participants will know which dose of insulin is being administered. Exceptions will be the study nurse who is directly involved in preparing the insulin.

## **15.4 Study Drug Dispensing**

Study drug will be dispensed by the study nurse.

## **15.5 Intranasal Administration**

Insulin will be administered with the Aptar CPS delivery device. This device release a metered insulin dose into the participant's nose, allowing the administration of smaller particle sizes to increase deposition in the upper nasal cavity while minimizing transport to the lungs. A volume of about 0.7 mL of insulin will be administered in each nostril, for a total volume of 1.4 mL per dose, 4 times daily.

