PRIMARY OBJECTIVE	We will test the hypothesis that 1 month of treatment with INI (40 IU q.i.d.), with the SGLT2i empagliflozin (empa; 10 mg q.d.), and with combined insulin plus empagliflozin (INI+empa) will result in safety profiles (number of treatment-related serious adverse events/primary outcome) that are similar to placebo.
SECONDARY OBJECTIVES	We will determine the effects of singular and combined therapy on AD cerebrospinal fluid biomarkers, cerebral blood flow (CBF) and cognition.
PRIMARY OUTCOME MEASURE	Number of treatment-related serious adverse events
SECONDARY OUTCOME MEASURES	PACC5, ADAS-Cog14, CSF A $\beta$ 40, A $\beta$ 42, total tau, and phospho-tau 181, whole brain CBF
STUDY DESIGN	Single-site, double-blind study
SAMPLE SIZE	n=60
SUMMARY OF KEY ELIGIBILITY CRITERIA	
 
Cognitively normal with positive amyloid (amyloid PET SUVR>1.21, CSF A<math>\beta</math>42<600 pg/ml)
 
Diagnosis of amnestic mild cognitive impairment (MCI) or early AD (CDR 0.5 or 1, MMSE>21)
 
Age: 55 to 85 years (inclusive)
 

DRUG DOSAGE & FORMULATION	40 International Units Humulin® R U-100 (Eli Lilly, Inc.) q.i.d.; empagliflozin (10 mg q.d.)
DURATION OF PARTICIPATION	8 weeks (4 weeks on active treatment)
PLACEBO	Insulin diluent (Eli Lilly, Inc.); cellulose capsule

ROUTE OF ADMINISTRATION	Intranasal (insulin); oral (empagliflozin)
PROCEDURES	Physical and neurological exam, nasal examination, cognitive testing, magnetic resonance imaging (MRI), continuous glucose monitoring, actigraphic sleep assessment, lumbar puncture, vitals, clinical labs, CSF and blood analysis and banking and APOE genotyping.

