## **2.4      Intranasal Delivery System Devices**

The intranasal delivery device to be used in this study has been developed and extensively tested by Aptar Pharmaceuticals, a company specializing in drug delivery. Specifications and instructions for the device are provided in attached materials:

- 1) The CPS pump is a multidose device utilizing an air-filtered preservative free system, in which a .2 micrometer filter membrane filters the airflow and insulin will be delivered through a spring loaded tip. This device is currently used in the delivery of Esketamine, a Janssen product approved by the FDA for the treatment of refractory depression.

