## **6.0 STUDY OVERVIEW**

The study will consist of a single site, randomized, double-blind trial comparing the effects of 4 weeks of INI (40 International Units q.i.d.), empa (10 mg q.d.) and combined INI and empa compared with placebo on CSF biomarkers and cognition. At study entry, participants will be randomized to one of 4 conditions: INI, empa, INI+empa, placebo. Participants who are cognitively normal but have abnormal elevations of brain amyloid (n=20) or who have MCI or early AD (n=40) will be enrolled. The primary outcome measure will consist of safety (treatment-related serious adverse events). Secondary measures will consist of CSF biomarkers, cognition, and cerebral blood flow. Exploratory measures will include continuous glucose levels and sleep quality as assessed with actigraphy.

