### **8.3 Baseline Visit 2 (Visit 3; one week after Baseline Visit 1)**

For the 2nd baseline visit which occurs one week after Baseline Visit 1, the following procedures will be administered:

- 1) Lumbar puncture will be performed in the morning after a minimum 8-hour overnight fast. After insertion of the spinal catheter, CSF will be collected immediately. Insulin (40 IU) will then be administered, additional CSF will be collected following administration, and then the spinal catheter will be withdrawn. Blood will be drawn immediately before and following the LP under fasting conditions. Participants will then receive a snack and instructions about post-lumbar puncture care. Site staff will call the participant within 24 hours from the lumbar puncture procedure to inquire about the participant's well-being and possible adverse events.
- 2) The ADCS-ADL-MCI and qDRS will be administered
- 3) The Libre Freestyle Pro continuous glucose monitor will be removed
- 4) The Empatica E4 actigraph and PROMIS sleep questionnaires will be collected
- 5) Device use and feasibility issues during the run-in period will be reviewed
- 6) Distribution of study drug and placebos (if applicable)
- 7) Nasal examination
- 8) Vital signs and weight
- 9) Collection of AEs and Con Meds

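### Section 15.5's 1.4 mL per dose does not match the 40 IU dose: at the stated U-100 strength it is 140 IU, 3.5 times too much, and no dilution is given

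*Combined protocol and SAP*

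**What the plan says.** The intended dose is consistent throughout. The synopsis gives "40 International Units Humulin® R U-100 (Eli Lilly, Inc.) q.i.d". Section 6.0 describes "4 weeks of INI (40 International Units q.i.d". Section 15.0 has participants take "four doses of INI (40 International Units per dose"), timed before meals and bedtime. The two lumbar puncture visits use the same amount: in Sections 8.3 and 8.7, "Insulin (40 IU) will then be administered".

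The strength is also explicit. Section 15.1 says that the product "contains human insulin (rDNA origin) 100 units/mL".

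The volume appears once, in Section 15.5: "about 0.7 mL of insulin will be administered in each nostril, for a total volume of 1.4 mL per dose, 4 times daily".

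Two further statements bear on how the insulin reaches the device. Section 15.3 exempts from the blind "the study nurse who is directly involved in preparing the insulin". Section 2.4 says "Specifications and instructions for the device are provided in attached materials". Insulin diluent is named only as the placebo, in the synopsis and in Section 15.2 (Randomization). No section gives a dilution step, a final concentration, a volume per spray or a number of sprays.

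**The concern.** Three quantities fix the delivered dose: the units intended, the strength of the solution and the volume sprayed. The protocol states all three, and they disagree. Section 15.5 calls the 1.4 mL insulin, and the synopsis identifies that insulin as U-100, so a reader who takes the text literally would load the undiluted product and exceed the dose.

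The primary outcome is the number of treatment-related serious adverse events at 40 IU four times daily. If the delivered dose is in doubt, so is the regimen that the safety result describes. An error of this kind would also repeat at every dose for four weeks. The supporting safety experience in Section 13.1 (Safety of Intranasal Insulin) stops well short of the literal reading: the repeated doses cited there are 40 IU four times daily for two months and 60 IU once daily for three weeks. The device study in Section 5.0 tested single doses of only 20 and 40 IU.

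**Working it through.** **Inputs**

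- Dose: 40 IU, four times daily (synopsis; Sections 6.0 and 15.0).
- Strength: 100 IU/mL (Section 15.1).
- Volume: 0.7 mL per nostril, 1.4 mL per dose (Section 15.5).
- Cited repeated-dose experience: 40 IU four times daily, and 60 IU once daily (Section 13.1, Safety of Intranasal Insulin).

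**Step 1. The plan's own sum.** 2 × 0.7 = 1.4 mL. The addition within Section 15.5 is correct.

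**Step 2. Units in the stated volume, undiluted.** Dose = volume × concentration = 1.4 × 100 = 140 IU. Ratio to the intended dose: 140 / 40 = 3.5. Per day: 140 × 4 = 560 IU, against 40 × 4 = 160 IU.

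**Step 3. Could rounding explain it?** The volume is approximate. Assume that the true value lies between 0.65 and 0.75 mL per nostril:

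- 2 × 0.65 = 1.3 mL, which is 130 IU (3.25-fold).
- 2 × 0.75 = 1.5 mL, which is 150 IU (3.75-fold).

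Rounding does not close the gap.

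**Step 4. Could a simple slip explain it?**

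- One nostril only: 0.7 × 100 = 70 IU.
- Misplaced decimal: 2 × 0.07 = 0.14 mL, which is 14 IU.

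Neither gives 40 IU.

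**Step 5. Volume that 40 IU needs, undiluted.** 40 / 100 = 0.4 mL per dose, or 0.2 mL per nostril.

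**Step 6. Concentration that 1.4 mL needs.** 40 / 1.4 = 28.6 IU/mL. That is 0.4 mL of U-100 plus 1.4 − 0.4 = 1.0 mL of diluent, a 3.5-fold dilution. No section states it.

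**Step 7. Against the cited experience, if undiluted.** Daily: 560 / 160 = 3.5 times the highest repeated daily dose in Section 13.1. Per administration: 140 / 60 = 2.3 times the highest single dose in repeated use there.

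| Reading | Volume per dose | Concentration | IU per dose | IU per day |
|---|---|---|---|---|
| Intended dose, undiluted U-100 | 0.4 mL | 100 IU/mL | 40 | 160 |
| Section 15.5 volume, undiluted U-100 | 1.4 mL | 100 IU/mL | 140 | 560 |
| Section 15.5 volume, diluted to fit | 1.4 mL | 28.6 IU/mL (not stated) | 40 | 160 |

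**The case against.** The best case for the plan is that nobody intends 140 IU. The 40 IU dose is repeated many times, and Section 15.0, not 15.5, is the dosing statement. Section 15.5 mainly describes a metered device, whose output and fill strength determine what is delivered. A nurse prepares the insulin and may dilute it. The device specifications are in attachments that could settle the spray volume. Section 5.0 also reports 40 IU given with this same device, so a working method probably exists, and a drafting slip is more likely than a planned overdose. Some neighbouring text looks carried over from a device or dose study: Section 15.3 refers to which insulin dose is given, although this trial has only one.

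Most of this stands, and it limits the claim. The 140 IU figure is conditional on undiluted loading, and the documents do not show that it would be delivered. The problem is also an inconsistency between sections rather than a faulty sum.

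It does not remove the conflict. Section 5.0 gives no volume or concentration, so it cannot reconcile Section 15.5. If the insulin is diluted, the final concentration is the figure needed to prepare and verify each dose, and it is absent. If the volume is a slip, it is a slip in the administration section for the study drug. Every reading leads to a change in the text.

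**Conclusion.** The concern holds and should be fixed before dosing. At the named product strength, Section 15.5's volume is 3.5 times what 40 IU requires: 140 against 40 IU per dose, and 560 against 160 IU per day. Taking 0.65 to 0.75 mL per nostril as the range of the approximation gives 130 to 150 IU, or 3.25- to 3.75-fold. These figures assume undiluted U-100. If the solution were diluted to about 28.6 IU/mL, the dose would be right and the defect would be an unstated concentration.

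Confidence is high that dose, strength and volume are unreconciled in the text. No claim is made about what participants would actually receive. Sample size, randomization and analysis do not depend on this point.

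**What to change.** Revise Section 15.5 so that volume times concentration equals 40 IU, in one of two ways:

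- **Undiluted U-100:** change the volume to about 0.4 mL per dose, about 0.2 mL per nostril.
- **Diluted insulin:** state the diluent and the final concentration in the device (about 28.6 IU/mL if 1.4 mL is kept).

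In either case, give the volume per spray and the number of sprays per nostril so that the dose can be verified. Then check the study nurse's preparation instructions and the device instructions against the corrected text.

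A separate, minor correction can go in the same amendment: Section 1.1 gives the treatment period as 4 months, whereas the synopsis says 1 month (4 weeks on active treatment) and Sections 1.0 and 6.0 say 4 weeks. Change it to 4 weeks.

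The cost is a text correction in Section 15.5, one word in Section 1.1 and a check of two sets of instructions. Visits, sample size and analysis are unchanged.

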## **15.6 Storage**

Insulin and empa will be maintained at a controlled temperature.

## **15.7 Drug Accountability**

The study nurse coordinator will maintain a log of study drug usage.

## **16.0 ADVERSE EVENTS**

### **16.1 Definition**

An adverse event (AE) is defined as per the Code of Federal Regulation Title 21 Part 312.

<http://www.accessdata.fda.gov/scripts/cdrh/cfdocs/cfcfr/cfrsearch.cfm?fr=312.32>

Adverse events which occur after informed consent is signed include but are not limited to: (1) worsening or change in nature, severity, or frequency of conditions or symptoms present at the start of the study; (2) participant deterioration due to primary illness; (3) intercurrent illness; and (4) drug interaction. An abnormal laboratory value will only be reported as an AE if the investigator considers it to be an AE, or if it leads to the participant being withdrawn from the study.

The investigator should attempt to establish a diagnosis of the event based on signs, symptoms, and or other clinical information. In such cases, the diagnosis should be documented as the AE and not the individual signs or symptoms. Symptoms and conditions present at the beginning of the study will be characterized, so that AEs can be defined as any new symptom, or any increase in frequency or severity of an existing symptom.

Following questioning and evaluation, all AEs, whether determined to be related or unrelated to the study drug by a medically qualified site PI or clinician (MD, DO, NP or PA), must be documented in the participant's medical records, in accordance with the investigator's normal clinical practice, and on the AE e-CRF. Each AE is evaluated for duration, severity, seriousness, and causal relationship to the study drug.

## **16.2 Following Up on AEs**

The investigator is obliged to follow participants with AEs until the events have subsided, the conditions are considered medically stable, or the participants are no longer available for follow up. Participants who discontinue due to adverse experiences will be treated and followed according to established medical practice. Adverse events will be rated as mild, moderate or severe. This will also pertain to abnormal laboratory values deemed clinically significant by the site clinician.

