## **8.7 Post-treatment Visit 2 (Visit 6; one week after Post-treatment Visit 1)**

On their second post-treatment visit which occurs 1 week after Post-treatment Visit 1 they will receive the following:

- 1) Lumbar puncture will be performed in the morning after a minimum 8-hour overnight fast. After insertion of the spinal catheter, CSF will be collected immediately. Insulin (40 IU) will then be administered, additional CSF will be collected following administration, and then the spinal catheter will be withdrawn. Blood will be drawn immediately before and following the LP under fasting conditions, including routine clinical laboratory evaluations. Participants will then receive a snack and instructions about post-lumbar puncture care. Site staff will call the participant within 24 hours from the lumbar puncture procedure to inquire about the participant's well-being and possible adverse events.
- 2) The ADCS-ADL-MCI and qDRS will be administered
- 3) The Libre Freestyle Pro continuous glucose monitor will be removed
- 4) The Empatica E4 actigraph and sleep questionnaire will be collected
- 5) Nasal examination
- 6) Vital signs and weight
- 7) Collection of AEs and Con Meds
- 8) Collection of nasal drug vials and pill count

Order of administration of procedures may occasionally vary due to scheduling constraints, as approved by the study clinicians.

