### **10.4 Clinical Laboratory Evaluations**

All routine laboratory samples will be analyzed by Laboratory Corporation of America (Labcorp). Lab reports will be reviewed, signed and dated by the study clinician. If a value is outside of the laboratory's normal range, the clinician will indicate if it is clinically significant or not. If clinically significant, lab tests may need to be repeated and follow up with the participant's PCP should occur.

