### **20.4 Data and Safety Monitoring Plan**

The principal investigator and study clinician(s) will be responsible for the overall monitoring of the data and safety of study participants, with assistance by members of the study staff. Participants will be screened at the beginning of the study and will be monitored carefully at each study visit. Participants will be queried for serious adverse events (SAEs) and selected AEs (those temporally related to study procedures) at each study visit. All SAEs and selected AEs will be recorded on an AE case report form. Based on the nature of the AE, study clinicians will determine the severity of the event and association with the study. All serious adverse events will be reported. Serious adverse events are defined as events that are (1) life-threatening or fatal, (2) result in severe or permanent disability, or (3) require hospitalization. SAEs will be reported to the IRB within 7 days of investigator

knowledge of the event if they are related and unanticipated (i.e. if they qualify as an unanticipated problem). All serious adverse events will be followed until resolution, or 90 days after study participation has been terminated.

"Severity" of events will be graded according to the following guidelines:

1. Mild: The participant is aware of, but can easily tolerate, the event
2. Moderate: The discomfort of the event is severe enough to interfere with some usual activities
3. Severe: The participant is incapacitated, and unable to perform most or all usual activities

The "study-relatedness" will be assigned according to the following guidelines:

1. Definitely Related: The reaction follows a reasonable temporal sequence and is known to be an effect of participation or a procedure
2. Possibly Related: The reaction follows a reasonable temporal sequence, and current medical knowledge does not preclude a relationship between participation or procedure and the event.
3. Unlikely: Little evidence to suggest a causal relationship (e.g. the event did not occur within a reasonable time after administration of the trial medication) or another reasonable explanation for the event (e.g. another clinical condition or other concomitant treatment).
4. Definitely Unrelated: Current medical knowledge precludes a causal relationship between participation or procedure and the event or the cause of the reaction is known to be other than participation or procedure.

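### Laboratory abnormalities are graded on a symptom-only severity scale, and the one scheduled clinical panel after take-home treatment starts has no planned summary by arm

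*Combined protocol and SAP*

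**What the plan says.** **Grading.** Section 16.2 states "Adverse events will be rated as mild, moderate or severe" and adds "This will also pertain to abnormal laboratory values deemed clinically significant by the site clinician". It does not define the grades. Section 20.4 does:

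- "Mild: The participant is aware of, but can easily tolerate, the event"
- "Moderate: The discomfort of the event is severe enough to interfere with some usual activities"
- "Severe: The participant is incapacitated, and unable to perform most or all usual activities"

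No numeric laboratory grade or threshold for grading appears anywhere in the document.

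**Becoming an adverse event.** Under section 10.4, when a result is out of range, "the clinician will indicate if it is clinically significant or not". Section 16.1 allows an abnormal value to be reported as an adverse event by two routes only: the investigator considers it one, "or if it leads to the participant being withdrawn from the study".

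**Recording.** Section 16.1 wants every adverse event on the electronic case report form, related or not. Section 20.4 asks only for serious events and selected others, namely those close in time to a study procedure.

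**Schedule.** Table 4 marks clinical labs at Visits 1, 3 and 6. Section 8.3 first hands out study drug at Visit 3. Section 8.7 describes the Visit 6 blood draw as "including routine clinical laboratory evaluations", and vials and pills are collected at that visit.

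**Analysis.** Section 12.0 covers treatment-related serious adverse events, CSF and plasma biomarkers, cognition and cerebral blood flow. It does not mention the clinical laboratory panel.

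**The concern.** The scale asks how the participant feels and functions. A laboratory change is often silent, and for a silent change the scale carries no information: a small deviation and a large one are treated alike. Nothing downstream makes up for this. Whether the value is listed as an adverse event is a clinician's decision, and no planned table shows the values themselves by arm.

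This matters because safety is the trial's primary aim. Section 5.2 says that no published work has examined empagliflozin's safety in Alzheimer's disease or in combination with intranasal insulin. The section on the safety of empagliflozin links one of its cautions to kidney function, which is a laboratory quantity, and mentions assessing it only at screening. A pilot meant to inform a later trial would be expected to report what its post-treatment panel showed in each arm. As written, the plan draws that panel and then relies on narrative adverse event reporting, with grades that do not fit.

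**Working it through.** No power, alpha or event rate is attached to this point, and section 12.1 says that no power calculation was done. The check is therefore a comparison of the rules and a count of the scheduled draws.

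**Step 1. Can a symptom-free laboratory change be graded?** Take a clinically significant change that the participant does not feel, and test it against section 20.4.

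| Grade | What section 20.4 requires | Met by a silent change? |
|---|---|---|
| Mild | Awareness, easily tolerated | Not literally, since there is no awareness |
| Moderate | Discomfort interfering with some activities | No |
| Severe | Incapacity | No |

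Literal matches: 0 of 3. The size of the deviation enters none of the definitions.

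**Step 2. What turns a laboratory value into an adverse event?** Section 10.4 requires a significant/not significant mark on each out-of-range value. Section 16.1 does not use that mark. It names investigator opinion or withdrawal. Withdrawal is a decision too, because the document gives no laboratory threshold for it. Both routes therefore rest on judgement. Section 16.2 then rates values marked significant, which section 16.1 need not treat as adverse events, and section 20.4 narrows what goes on the form.

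**Step 3. Where do the scheduled panels fall?**

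- Scheduled clinical panels in Table 4: 3 (Visits 1, 3 and 6).
- Before take-home treatment or at its start: 2 (Visits 1 and 3).
- After take-home treatment starts: 3 − 2 = 1 (Visit 6).

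Visit 5 is not dated, and Visit 6 follows it by one week. Treatment lasts 4 weeks.

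- If Visit 5 is at treatment week 3, Visit 6 is at week 3 + 1 = 4, the end of treatment. The section on the safety of combined insulin and empagliflozin implies this, because it places glucose sensor wear in the last treatment week and the sensor is fitted at Visit 5.
- If Visit 5 is at week 4, as its post-treatment name implies, Visit 6 is at week 4 + 1 = 5, and the panel is drawn after the 4 weeks.

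In both cases Visit 6 is the only scheduled panel that can show a change after take-home treatment starts.

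**Step 4. Is that panel analysed?** Section 12.0 plans no by-arm summary of clinical labs. Its plasma biomarker analyses could cover the fasting insulin and glucose of section 11.2, but nothing in it reaches the rest of the panel. With 60 participants and equal allocation to four arms, a by-arm table would describe up to 60 / 4 = 15 people per arm.

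**Step 5. Does this touch the primary outcome?** The synopsis and sections 1.1, 6.0 and 12.0 make it the number of treatment-related serious adverse events. Seriousness (sections 17.1 and 20.4) and relatedness decide that count; the mild/moderate/severe grade does not. Section 5.2, however, words the primary outcome as treatment-related adverse events, without limiting it to serious ones. On that wording, the rule for calling a laboratory value an adverse event would feed the primary count.

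**The case against.** Several stronger readings are tempting, and the documents do not support them.

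- **That laboratory harm cannot be registered.** It can. The investigator route in section 16.1 works at Visit 6, and section 10.4 requires each report to be reviewed and signed and each out-of-range value to be marked. What remains is that capture is discretionary and the grade uninformative.
- **That withdrawal is the one objective trigger and never operates on treatment.** Withdrawal is itself a judgement. It could follow repeat labs under section 10.4, Visit 3 results that come back after dosing has begun, or the glucose checks that the section on combined safety promises at all visits. Table 4 and the Visit 4 and 5 lists show no blood draw for those checks, so these places conflict and must be reconciled, but the route cannot be ruled out.
- **That silent changes will always be recorded as mild.** Section 20.4 calls its grades guidelines and lets clinicians judge by the nature of the event, and section 16.1 prefers a diagnosis to an isolated finding. A clinician could depart from the wording. Any such departure would have no rule to follow and could differ from case to case.
- **That the primary result is distorted.** Under the serious-event definition it is not. A laboratory change that needs hospitalisation counts as serious whatever its grade.
- **That an assumed rate of silent changes gives the size of the problem.** The documents give no rate. The chance that at least one such change occurs is also not the chance that it is missed or misgraded.

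It can also be said that the last sentence of section 16.2 sits under a heading about following up adverse events and may mean only laboratory values already accepted as such. That is a fair reading and softens the mismatch with section 16.1, but those values still have to be graded on the same scale. Lastly, the clinical panel is not itemised, so kidney function at Visit 6 cannot be assumed.

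**Conclusion.** The point holds in a limited form. The plan puts laboratory values on a scale that does not describe them: a symptom-free change of any size cannot meet moderate or severe. Adverse event status for such a value depends on clinician judgement, and the sections on what is recorded disagree. One of the three scheduled clinical panels falls after take-home treatment starts, in up to 60 participants, and section 12.0 leaves it without a by-arm summary.

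The consequence is a weaker account of non-serious laboratory safety. The count of treatment-related serious adverse events does not change unless the wording in section 5.2 governs. The conclusion rests on the stated grade definitions and on Table 4; it does not depend on any assumed event rate or on whether Visit 6 is at week 4 or week 5. How many values would be misgraded or left out cannot be estimated from the documents.

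**What to change.** 1. **Sections 16.2 and 20.4:** grade laboratory values by a published numeric laboratory grading table, named and fixed before unblinding. Keep the symptom scale for clinical events. For any analyte that the table does not cover, report the change only.
2. **Section 12.0:** tabulate by arm the Visit 3 to Visit 6 change and grade shift for every clinical laboratory test already drawn, whether or not the value was called an adverse event. This step does not depend on judgement. Making every value marked significant an adverse event would not achieve the same, because the mark is itself a clinician's opinion. Section 8.3 does not list the Visit 3 clinical panel that Table 4 shows, so confirm that it is drawn.
3. **Reconcile** sections 16.1, 16.2 and 20.4 on which laboratory values and adverse events are recorded; the section on combined insulin and empagliflozin safety with Table 4 on glucose monitoring; and section 5.2 with the other statements of the primary outcome.

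The cost is a few sentences, one more table and a few more graded values. No new blood draw is needed. With about 15 people per arm the table is descriptive and should be labelled so.
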